A 2007 study by Narayanaswamy et al. demonstrated a difference between the generic and original versions of Latanoprost. This pilot study involving 30 patients in a single center in India seemed to demonstrate that generic Latanoprost was less effective than Xalatan in lowering IOP. [8]. However, this is only a small study and some questions about the reliability of the results have surfaced, including concerns regarding the improper storage of the generic Latanoprost used.

On the other hand, several studies have shown an equivalence between the generic drug and the original. A randomized, double-blind study in 2011 by Diguini et al., involving 184 patients, demonstrated the non-inferiority of a generic version of Latanoprost compared to Xalatan.[9]. On the other hand, the generic version used in this study had a composition qualitatively and quantitatively identical to Xalatan, which is often not the case [4][10]. Another randomized multicentre study, by Allaire et al., included 266 patients with diagnosis of primary open angle glaucoma and ocular hypertension. Each patient was assigned to the generic Latanoprost group or the Xalatan group in a ratio of 1: 1. This study demonstrated therapeutic equivalence as well as the same safety profile [11]. Finally, a randomized crossover study by Golan et al. in 2015, compared Glautan, a generic version of Latanoprost, to Xalatan in 19 patients. The hypotensive effect and ocular side effect profile was comparable [12].

2. Objectives

The primary goal was to determine if generic Sandoz-Travoprost is as effective as brand Travatan Z in lowering intraocular pressure, as measured using Goldmann applanation tonometry.

The secondary goal was to determine if patients tolerate generic Sandoz-Travoprost as well as brand Travatan Z, using a questionnaire.

3. Methodology

a. Study Design

Randomized controlled clinical trial, unblinded, crossover trial.

The crossover design was chosen to achieve the power required all the while limiting the number of patients required.

This study was not blinded to reproduce as much as possible the real situation experienced in clinic by the patients and the doctors. The use of masked bottles by the pharmacy was considered. However, some studies have suggested that the different characteristics of drop bottles may have an impact on the size of the drop or the concentration of the drug after 30 days[14]. So it was decided to use the original bottles.

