b. Information on the medication used in the study [15]

The two drugs in the study are the original Travoprost (Travatan Z) and the generic Travoprost. Both are approved in Canada for hypotensive therapy in patients with GPAO or HTO. They are available in solution in 5 mL bottles. Since there are several companies that produce generic Travoprost, we would choose a version that will be the same for the entire study.

i. Mechanism of action:

Selective FP prostanoid receptor agonist that decreases intraocular pressure by increasing uveoscleral drainage.

ii. Posology and administration:

The recommended dosage is a drop in the affected eye or eyes once a day. The optimal effect is obtained by administering it in the evening. The instillation rate of Travatan Z ophthalmic solution (Travoprost) should not exceed 1 time / day, as it has been demonstrated that a higher frequency may decrease the reducing effect of intraocular pressure.

The reduction in intraocular pressure begins approximately 2 hours after instillation and reaches its maximum after 12 hours.

Storage between 2 ° C and 25 ° C recommended for stability.

iii. Ingredients:

Active ingredient: Travoprost 0.040mg/mL

Other ingredients: Sofzia (preservation system with boric acid, propylene glycol, sorbitol, zinc chloride), polyoxyethylenated hydrogenated castor oil 40 and purified water. A very small amount of hydrochloric acid or sodium hydroxide is added to maintain the pH at the appropriate value.

iv. Ocular adverse effects

> 10% :

Changes affecting eyelashes such as increased eyelash length and increased eyelash thickness (61%), ocular hyperaemia (30-50%)

1% to 10% :

Decreased visual acuity (5% to 10%), ocular discomfort (5% to 10%), eye pain (5% to 10%), eye pruritus (5% to 10%), blepharitis (1% to 4%), impaired vision (1% to 4%), cataracts (1% to 4%), conjunctivitis (1% to 4%), corneal staining (1% to 4%), crusting eyelids (1% to 4%), dry eye syndrome (1% to 4%), eyelid hyperpigmentation (periorbital, 1% to 4%), hyperpigmentation of the iris (1% to 4%), keratitis (1% to 4%), tearing (1% to 4%), ophthalmic inflammation (1% to 4%), photophobia (1% to 4%), subconjunctival hemorrhage (1% to 4%)

Post-marketing and / or case reports :

Bacterial keratitis (due to contamination of solution), corneal edema, cystoid macular edema, iritis, macular edema

v. Systemic adverse effects

> 10% :

None reported

1% to 10% :

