- Use of other hypotensive ophthalmic drops (except for Travatan Z or generic Travoprost)
- Use of corticosteroid
- To be pregnant
- Breast-feed
- Being monocular
- Have had glaucoma surgery such as trabeculectomy and Tube implants (eg Baerveldt, Ahmed). Patients who have had selective laser trabeculoplasty will also be excluded.
- Active intraocular inflammation
- Ocular surface disease that may interfere with an accurate measurement of IOP
- Any clinically significant eye disease that may interfere with the study

6. Recruitment

The subjects will be adult patients seen in the outpatient ophthalmology clinic of the Hotel-Dieu de Sherbrooke, who require or already use a pharmacological treatment of Travoprost original (Travatan Z) or generic Travoprost and meeting the eligibility criteria.

The subjects will be recruited at the outpatient ophthalmology clinic of the Hôtel-Dieu de Sherbrooke after a new consultation or a follow-up appointment. The physician resident will present the study to the patient, complete the consent form and obtain their signature.

The randomization will be done beforehand.

The only inconveniences for patients, no matter what group they are in, are the 2 follow-up visits, one to 3 weeks and one to 6 weeks.

7. Variables and data collection

Variable	Type	Method of measurement
age	continuous	From the chart
sex	dichotomous	From the chart

ethnic group	categorical	From the chart
diagnostic	categorical	From the chart
IOP	continuous	Goldmann applanation tonometry
initial treatment	dichotomous	From the chart
MD (visual fields)	continuous	Visual field; at the initial appointment
side effects	dichotomous	questionnaire; at the 3 week and 6 week appointments
treatment adherence (number of days missed)	continuous	questionnaire; at the 3 week and 6 week appointments

The data will be collected by the resident in charge of the project, who will be responsible for their management. Registration will be in accordance with the accepted standards of confidentiality as described in the Act respecting health services and social services.

We will use the Goldmann tonometer, a device on the slit lamp, to measure intraocular pressure. Currently, she is the gold standard for measuring intraocular pressure[13].

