At the follow-up visit, if the patient qualifies for the study, resident [name] will present the study. If the patient agrees, resident [name] will complete the consent form with the patient and get his signature. The sociodemographic data of the patient will be collected and a complete ophthalmological examination will be performed. This examination will include visual acuity, external examination, evaluation of the cornea, anterior chamber, iris, lens, anterior vitreous, retina and optic nerve (with pharmacological dilatation). Intraocular pressure, gonioscopy, pachymetry and visual field Humphrey SITA Standard 24-2. Gonioscopy, pachymetry and the visual field could be delayed if they were done in the previous 4 months. The patient will receive a bottle of original Travoprost (Travatan Z) or generic Travoprost according to the prior randomization. The patient will receive explanations on how to put the drops.

During the second visit, at 3 weeks +/- 3 days, the IOP will be taken by resident [name] at the same time as the first visit +/- 1h. A bottle of the other medicine will be given to him.

At the third visit at 6 weeks +/- 3 days, the IOP will be taken by resident [name] at the same time as the first visit +/- 1h. The patient will have finished the study and a prescription of his starting medication will be given.

A questionnaire on tolerance and comfort of drops will be completed with the patient at the second and third visit.

c. For patients who drop out of the study or who are lost to follow-up:

A loss of follow-up of 10% is anticipated so the sample size has been increased by 10%.

d. Management of adverse effects:

The adverse effects of these drugs are well known and are mostly minor and transient. A questionnaire on tolerance and comfort of drops will be completed with the patient at the second and third visit. If, however, a patient is very concerned about an adverse reaction, they may contact the ophthalmology outpatient clinic or contact the resident on call.

Table: Summary of 3 visits by group

	Recruitment day (day 0)	Second visit (at 3 weeks)	Third visit (at 6 weeks)

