
Group 4 (Patient already randomized to receive generic Travoprost first)
	
 • Presentation of the study to the patient • Obtaining consent • A bottle of generic Travoprost given with instruction to instill a drop at bedtime in the eye reaches 	
 • IOP taken by the resident • Complete the questionnaire on the comfort of the treatment • A bottle of Travoprost original (Travatan Z) given with instructions to instill a drop at bedtime in the eye reaches 	
 • IOP taken by the resident • Complete the questionnaire on the comfort of the treatment • End of the study

9. Data analysis

The database will be created with Microsoft Excel.

Statistical calculations will be done with SPSS v20.

a. Comparison of the composition of the different groups

A t-test will be used for continuous variables (if the data are not normally distributed, a Mann-Whitney test will be used).

A Chi-square test will be used for categorical variables (if the frequency is less than 5 for a variable, an exact Fisher test will be used).

b. Comparison of groups at the end of the study

A paired t test will be used if the data is normally distributed (otherwise, a Wilcoxon test will be used).

c. Analysis of the therapeutic effect of drugs

An ANOVA test will be used to compare the effect of the treatments over time (an appropriate transformation will be applied to the data if it is not normally distributed).

d. Comparison of adverse effects between the two treatments

A McNeman test will be used to see if each side effect is as common with both treatments.

e. Comparison of compliance with each treatment

A paired t test will be used to see if patients have the same compliance for each treatment (Wilcoxon test if non-normal data).

10. Limitations

There is a potential bias of information if a patient believes that the generic is less effective, which could lead to a decrease in compliance or a change in dosage by the patient (eg: he could put it twice a day and not once). To counter this bias, the importance of abiding by the prescribed posology will be explained to patients.

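### Side effects asked only at weeks 3 and 6, without a day-0 questionnaire or a gap between products, cannot be attributed to a product when they last beyond three weeks

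*Combined protocol and SAP*

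**What the plan says.** The objective in section 2 reads: "The secondary goal was to determine if patients tolerate generic Sandoz-Travoprost as well as brand Travatan Z, using a questionnaire". The variables table in section 7 lists side effects as dichotomous, with the source "questionnaire; at the 3 week and 6 week appointments". Sections 8a and 8b agree: "A questionnaire on tolerance and comfort of drops will be completed with the patient at the second and third visit". In the visit table that closes section 8, the day-0 column has no questionnaire for any of the four groups.

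At week 3 the patient changes product with no interval described: "A bottle of the other medicine will be given to him". Section 6 admits patients "who require or already use a pharmacological treatment of Travoprost original (Travatan Z) or generic Travoprost", so Groups 3 and 4 start the trial already exposed to one of the two products.

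The analysis in section 9d is one test per effect: "A McNeman test will be used to see if each side effect is as common with both treatments". It has no term for day-0 status, period or order, and no rule separating a new effect from a continuing one. Section 10 does not discuss persistence of side effects.

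On duration, section 3b iv lists eyelash changes (61%) and iris and eyelid hyperpigmentation (1% to 4% each). Section 8d describes the effects as mostly minor and transient.

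**The concern.** McNemar's test uses only patients whose answers differ between the two products. If an effect was there before day 0, or began on the first product and is still visible three weeks after the switch, the patient answers yes twice. That pair drops out of the comparison, whichever product caused the effect.

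For such items the crossover loses the feature it relies on, a return to the starting state before the second period. With balanced orders the estimated difference shrinks towards zero, and zero is the result that the secondary objective hopes to support. An interval or a margin would not repair this, because the estimate itself is shrunken. The comparison also matters to the rationale: the introduction says that different non-medicinal ingredients may alter the type and frequency of adverse effects.

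**Working it through.** **Plan's own figure.** The plan gives no rate, difference or power for side effects. Its 69 patients (69 × 1.1 = 75.9, so 76 with losses) are sized for intraocular pressure. I use 69 only as the number of complete pairs.

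**Inputs from the plan.** Dichotomous item at weeks 3 and 6 (section 7); direct switch (section 8); mixed treatment status at entry (section 6); McNemar's test (section 9d). Section 6 says that randomization is done in advance, but no allocation ratio or blocking is given.

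**Assumed inputs (the documents give none).**
- pA, pB: probability that each product causes the effect in a three-week period.
- s: probability that an effect starting in period 1 is still scored at week 6 because it persists.
- b: share of all patients with the effect at day 0 and through both periods.

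**Expected difference, A minus B, when b = 0.**
- A first: pA − [pB + s·pA(1 − pB)].
- B first: [pA + s·pB(1 − pA)] − pB.
- Mean of two equal-sized orders: (pA − pB) − (s/2)[pA(1 − pB) − pB(1 − pA)] = (pA − pB)(1 − s/2).
- Patients affected throughout contribute zero, so the result is multiplied by (1 − b).

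Observed difference = (pA − pB)(1 − b)(1 − s/2).

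**Results for an assumed true difference of 20 points** (exact two-sided McNemar at 0.05, 69 pairs, independent onset):

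| b | s | Observed difference | Power, 30% v 10% | Power, 50% v 30% |
|---|---|---|---|---|
| 0 | 0 | 20 points | 79% | 60% |
| 0 | 0.5 | 20 × 0.75 = 15 | 65% | 46% |
| 0 | 1 | 20 × 0.5 = 10 | 42% | 30% |
| 0.25 | 0.5 | 20 × 0.75 × 0.75 = 11.3 | 49% | 34% |
| 0.5 | 1 | 20 × 0.5 × 0.5 = 5 | 14% | 12% |

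The first row is the fully transient case, with no loss. As a check on the discordant cells for 30% v 10% with b = 0: at s = 0 they are 0.3 × 0.9 = 0.27 and 0.1 × 0.7 = 0.07, difference 0.20. At s = 1 each is halved to 0.135 and 0.035, difference 0.10.

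**Unequal orders.** Take no true difference, both rates 30%, s = 1, b = 0, and an assumed 60:40 split. A-first patients contribute −0.3 × 0.7 = −0.21 and B-first patients +0.21. The expected difference is 0.6 × (−0.21) + 0.4 × 0.21 = −0.042. A spurious 4.2 points is charged to the product more often given second.

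**The case against.** The strongest reply is that the affected items may be few or absent. The questionnaire is not in the documents. Section 7 says only that it lists effects patients can easily identify and is completed verbally, and elsewhere it is described in terms of tolerance and comfort. The 61% and the pigmentation effects come from the drug-information list in section 3b iv. Section 8d expects mostly transient effects, and the documents give no reason to expect a 20-point difference in lash growth between products with the same active ingredient and concentration. All of this stands. It limits the point to items that are both on the questionnaire and lasting. It does not remove the point, because mostly is not always, and no reference period or new-onset rule is written.

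A reader might infer more than the documents support:

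- *That every lasting effect is charged to both products.* An effect that first appears in period 2 is charged only to the second product. This is why full persistence halves the difference and does not abolish it.
- *That the bias always runs towards equality.* That requires balanced orders, which the plan does not state.
- *That the 61% can be entered as b.* That gives 20 × 0.39 × 0.5 = 3.9 points, but only if every patient was previously treated and 61% of them were affected. If half were previously treated (assumed; no split is given), b = 0.305 and the result is 20 × 0.695 × 0.5 = 7.0 points.
- *That nothing is recorded at day 0.* A complete eye examination, including the external eye and iris, is done in both entry routes. However, section 9d makes no use of it.

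It is also tempting to rescore every item as new or worse since the current bottle. That would harm the transient items, which need no correction. A patient who reacts to both products would become a false discordant pair. With 69 pairs, assumed transient rates of 50% v 30%, 25% reacting to both, and a continuing effect not scored again, the discordant cells move from 0.25 v 0.05 to 0.375 v 0.175 and power falls from 86% to 56%. In an open-label trial, asking about worsening also invites patients' expectations about generics, which section 10 already raises.

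**Conclusion.** The concern holds for any questionnaire item that lasts beyond three weeks, and only for those. For such items the comparison in section 9d is multiplied by (1 − b)(1 − s/2) when the orders are balanced. Under full persistence with nobody affected at day 0, an assumed 20-point difference becomes 10, and power falls from 79% to 42% (30% v 10%) or from 60% to 30% (50% v 30%). With unequal orders, persistence can produce a difference where none exists. Fully transient effects are unaffected.

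The structural facts (timing, scoring, direct switch, entry of treated patients, test) are in the plan. The rates, b, s and the presence of lash or pigment items on the questionnaire are assumptions, so the sizes are illustrations and not estimates for this trial. The outcome is secondary, and the primary pressure comparison is not touched by this point.

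**What to change.** 1. Complete the same questionnaire at the existing day-0 visit in all four groups.
2. Keep the present/absent McNemar test in section 9d for transient and comfort items, with each item worded to refer to the current bottle. Do not rescore all items as new or worse.
3. List in advance the items that can last. For these, replace the McNemar comparison with a between-group comparison at week 3 in new consultations (Group 1 v Group 2), reported descriptively. Use the day-0 answers to separate pre-existing effects in Groups 3 and 4.
4. Limit the conclusion on the secondary objective in section 2 to transient effects and comfort.

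A day-0 questionnaire alone deals only with b. The week-3 comparison is needed to remove s.

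The cost is a few minutes at day 0, with no added visit or procedure, and a narrower tolerability claim. The week-3 comparison will be imprecise. If half of the 69 were new consultations split evenly (assumed), about 17 per group, then at 30% v 10% the 95% half-width is 1.96 × √(0.21/17 + 0.09/17) = 0.26, or 26 points. If data have already been collected, the day-0 step is no longer possible; the week-3 comparison and the narrower conclusion still are, and the limitation should be stated.

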The questionnaire given to patients will be a home-based questionnaire designed to check whether patients have had difficulty putting the drops, if they forget to put them on and if they have had adverse effects. The questionnaire will contain a list of side effects that patients can easily identify. The questionnaire will be filled verbally with the patient, and not just read and checked.

The mean deflection index (MD), a parameter given by the automated visual field, is an accepted measure in the literature for stratifying the glaucoma stage, either mild, moderate, or advanced [13].

8. Study Protocol

a. For patients who are new consultations:

At the first visit, the patient's sociodemographic data will be collected and a complete ophthalmic examination will be performed. This examination will include visual acuity, external examination, evaluation of the cornea, anterior chamber, iris, lens, vitreous, retina and optic nerve (with pharmacological dilatation). Intraocular pressure, gonioscopy, pachymetry and visual field Humphrey SITA fast 24-2. If the patient qualifies for the study, resident [name] will present the study. If the patient agrees, resident [name] will complete the consent form with the patient and get his signature. The patient will receive a bottle of original Travoprost (Travatan Z) or generic Travoprost according to the prior randomization. The patient will receive explanations on how to apply the drops.

During the second visit, at 3 weeks +/- 3 days, the IOP will be taken by resident [name] at 9:00 +/- 1h. A bottle of the other medicine will be given to him.

At the third visit at 6 weeks +/- 3 days, the IOP will be taken by resident [name] at 9:00 +/- 1h. The patient will have completed the study and a prescription from Travoprost will be given.

A questionnaire on tolerance and comfort of drops will be completed with the patient at the second and third visit.

b. For patients who were already followed and treated with brand Travoprost (Travatan Z) or generic Travoprost:

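### The protocol foresees twice-daily use of a distrusted generic, but adherence is recorded only as missed days, so over-use has no planned measurement or analysis

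*Combined protocol and SAP*

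**What the plan says.** Section 10 (Limitations) opens with this risk: "There is a potential bias of information if a patient believes that the generic is less effective". Two routes are named, lower compliance and a self-made dosage change. The example given for the second is that "he could put it twice a day and not once". The stated counter-measure is that "the importance of abiding by the prescribed posology will be explained to patients".

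Section 3b ii (Posology and administration), in a sentence about Travatan Z, says that "it has been demonstrated that a higher frequency may decrease the reducing effect of intraocular pressure".

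The variables table in section 7 lists "treatment adherence (number of days missed") as a continuous variable, taken by questionnaire at the 3-week and 6-week visits. The text of section 7 describes the questionnaire as a means to "check whether patients have had difficulty putting the drops, if they forget to put them on and if they have had adverse effects". It is completed verbally with the patient. Section 9e compares compliance between the two products with a paired t test, or a Wilcoxon test if the data are not normal.

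No item on dosing frequency, no diary, and no return or weighing of bottles is described.

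**The concern.** The plan names a deviation and then chooses an adherence measure that cannot register it. Missed days capture under-use. Over-use leaves that count at zero.

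Three features of the trial make this more than a gap in record-keeping:

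- Section 3a makes the trial unblinded, so patients know when they are on the generic, and a belief about the generic can act in that period only.
- By the protocol's own account, more frequent dosing may reduce the effect on intraocular pressure (IOP), which is the primary outcome.
- Section 12 says that a finding of lesser efficacy would lead the team to make sure that patients receive the brand. A difference produced by over-use would feed that decision.

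Section 9e could meanwhile report equal compliance on both products, which a reader would take as evidence that the bias named in section 10 did not occur.

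**Working it through.** No figure stated in the plan bears directly on this point. The sample size (69, raised to 76) is not an input. The 1.5 mmHg difference in section 5 serves below only as a yardstick.

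**1. What the adherence variable records.** Let M be the number of days in a period with no drop. Take a 21-day period on each product (section 8: visits at 3 and 6 weeks).

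| Patient | On the brand | On the generic | M, brand | M, generic | Paired difference in M |
|---|---|---|---|---|---|
| A | once every day | once every day | 0 | 0 | 0 |
| B | once every day | twice every day | 0 | 0 | 0 |
| C | once every day | misses 5 days | 0 | 5 | 5 |

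B has 21 extra instillations per treated eye on the generic and contributes the same value to section 9e as A. C, who shows the reduced-compliance route, is picked up. The measure works for one route and is blind to the other. (The 5 days are illustrative.)

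**2. Whether the crossover removes the effect.** Write D = IOP on generic − IOP on brand. For a patient in either sequence,

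D = τ ± π + δ·O + error,

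where τ is the product difference, π the period effect (its sign depends on the sequence), O = 1 if the patient over-uses the generic only, and δ is the resulting change in IOP. Averaged over two sequences of equal size, π cancels and the mean is τ + p·δ, with p the proportion who over-use. If some patients over-use the brand too, with the same δ, the bias is (p_generic − p_brand)·δ. Behaviour that follows the product therefore stays in the estimate, while behaviour common to both products drops out.

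**3. Direction.** If higher frequency weakens the effect, then δ > 0, IOP on the generic is higher, and the bias runs against the generic. Section 3b ii says only that this may happen, and says it of Travatan Z. Carrying it over to the generic is an inference.

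**4. Size.** Neither p nor δ is in the documents. With both assumed, p from 5% to 30% and δ from 1 to 3 mmHg:

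- lowest: 0.05 × 1 = 0.05 mmHg, and 0.05 / 1.5 = 3% of the planning difference;
- highest: 0.30 × 3 = 0.9 mmHg, and 0.9 / 1.5 = 60% of it.

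The range runs from trivial to important. It shows that the size is unknown, not that it is large.

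**5. Whether running out of drops would reveal it.** Section 15 budgets one generic bottle per patient, of 5 mL. Twice-daily use in both eyes takes 21 × 2 × 2 = 84 drops over 21 days and 24 × 2 × 2 = 96 over 24 days. Drop size is not in the documents; at an assumed 25 to 50 microlitres, 5 mL holds 5000/50 = 100 to 5000/25 = 200 drops. The longest second period that the visit windows allow is 45 − 18 = 27 days, which takes 108 drops and exceeds the supply only near the largest drop size. Use in one eye takes half as much. Running out is not a reliable signal.

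**The case against.** The strongest case on the other side has five parts.

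*Over-use is only an example.* A reader might infer that the protocol treats twice-daily use as its main bias. It does not. It is one illustration within one potential bias, listed beside a learning bias and loss to follow-up, with no ranking. This stands.

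*Much of the bias is covered.* A reader might also infer that the distrust bias as a whole goes unexamined. That is not so: lower compliance is recorded at both visits and tested in section 9e. Nor can it be said that over-use could never come to light. The interview is verbal, it asks about difficulty with the drops, and the form itself is not in the documents. What stands is narrower: no variable and no analysis is planned for over-use.

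*Prevention is more than one sentence.* The summary table in section 8 has the bedtime one-drop instruction given with each bottle, including at the switch, and section 10 adds teaching or checking of technique at the first visit. This is true, but it is all instruction. None of it measures whether the instruction was followed.

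*Direction and size are not established.* The protocol's wording is conditional, and any figure in mmHg is a product of two guesses. This stands in full, and the severity should not rest on such a figure.

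*The trial is meant to resemble practice.* Section 3a leaves the trial open to reproduce clinical conditions, so one could argue that over-use prompted by belief is part of the real-life effect. But section 10 itself calls the behaviour a bias to be countered. Even on the pragmatic view, readers would need to know how often it happened in order to interpret a difference.

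**Conclusion.** The point holds as a measurement gap. The protocol foresees over-use of the generic and says that higher frequency may reduce the IOP effect, but it defines adherence so that a daily double-doser counts as fully adherent. Section 9e can therefore reassure falsely on this route, while it remains informative on missed days.

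The possible effect on the IOP comparison is a shift of (p_generic − p_brand)·δ, plausibly against the generic. This rests on two assumptions: that over-use is more common on the generic, and that the statement about Travatan Z applies to the generic as well. The size cannot be derived from the documents. The assumed range of 0.05 to 0.9 mmHg is illustration only.

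The documents do not support the stronger conclusion that the trial's result would be biased, or biased by a material amount. This is a worthwhile, nearly free improvement, and it does not put the design in doubt.

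**What to change.** 1. **Section 7.** Add a row to the variables table, number of days with more than one instillation (continuous, questionnaire at weeks 3 and 6), and add the matching question to the questionnaire.
2. **Section 9e.** Compare this variable between products alongside missed days, and report the paired difference with its confidence interval. Most values may be zero, so also give the number of patients with any such day on each product; the Wilcoxon alternative already in 9e would then be likely to apply.
3. **Optional.** Add a supportive IOP sensitivity analysis that excludes patients whose over-use exceeds a pre-specified number of days in either period, with the all-patients analysis kept as primary. A threshold per period is needed because IOP is measured once per product, so single days cannot be removed. Excluding one period removes the whole pair, and the exclusion depends on behaviour after randomisation, so this analysis can only be supportive.

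**Cost.** One question in an interview already held at both visits, and one data column. No dose or clinical rule changes. The limitation is that the answer is self-reported to the resident who gave the instruction, so over-use may be under-reported. A difference between products would be informative; the absence of one would be only weak reassurance.
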